11. PROCEDURES INVOLVED*

Randomization. Two groups of two practices (4 practices in total) will be matched based on comparable size and percent of minority patients. Within each pair, practices will be randomly allocated to Asthma Link or the comparison condition, using a computerized function. This will result in two practices randomized to the Asthma Link condition and two practices randomized to the Enhanced Usual Care comparison condition.

Recruitment will be performed from each practice site until the target n=72 parent-child dyads (18 per site) are recruited. (see section 13 on “Sample size calculation”) Recruitment will begin during the 2021-2022 academic school year.

Procedure Steps:

1. Research coordinator (RC) identifies potentially eligible patients (children aged 6-17 years (enrolled in grade 1-12) years and prescribed a daily inhaled corticosteroid per medical record from most recent visit scheduled for a clinic visit) through the practice's office scheduling and medical record system (e.g., Epic). RC will also collect that patient's name, DOB, mailing and email addresses, phone number, insurance type (as a proxy for socioeconomic status), list of

INVESTIGATOR STUDY PLAN

medications, number of emergency room visits, number of hospital admissions and number of oral steroid courses for asthma relief.

2. RC creates a Lilac Form for any potentially eligible patients as described above. (Lilac form is an indicator to the medical provider seeing the patient that this patient is potentially eligible for study.)

3. Asthma Link condition: As part of clinical practice, medical provider will determine if patient is struggling with taking daily asthma medicine. If YES, then will introduce Asthma Link by saying “There is a clinical program that allows for your child to receive their daily asthma medicine at school supervised by the school nurse.” Child can be enrolled in Asthma Link per the usual clinical steps (see Asthma Link steps).

- After they are enrolled in Asthma Link, medical provider will give family one-page description of study (see Flyer) and state “Researchers at UMass are performing a study of children who are participating in Asthma Link, would you be interested in hearing more?”

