12. DATA AND SPECIMEN BANKING*

N/A

13. Data Analysis and Management*

Sample size calculation

In order to obtain a sample size of 72 parent-child dyads to complete the research, we will potentially enroll up to 100 parent-child dyads. Because pilot studies do not provide meaningful estimates of effect sizes for between-condition comparisons, due to the imprecision inherent in data from small samples^{19,20} we base our proposed sample size of 72 parent-child dyads (36 per condition, 18 per practice) on pragmatics of recruitment, retention and the necessities for examining feasibility, providing important information for design and recruitment for the future R01 study to test the impact of Asthma Link™ in a large cluster RCT. We will identify refinements required to implement the large cluster RCT by obtaining data about several process outcomes as well as feasibility of recruitment, retention, engagement, fidelity and assessment procedures of Asthma Link™.

Taking estimation of retention rate as an illustrative outcome, and applying an intra-class (pediatric practice) correlation of 0.01, similar to the value of 0.006 from [name] prior studies of school-based teen smoking, the resulting design effect= $1.19 = 1 + [1 + 0.01 \times 9]$ ²¹ yields an effective sample size of $20/1.09 \approx 18$ dyads/condition. For a conservatively low retention rate of 80%, lower than the 97% observed in [name] previous FITLINE study,¹⁸ we can estimate a 95% confidence interval for retention percent of (51.9%, 95.7%) for each practice separately or (68.9%, 88.5%) combining all 4 practices. A sample of 18 dyads per practice (36 per condition) yields 95% confidence intervals for practice ICC of (0.018, 0.094) for a conservatively large true ICC=0.05.²² Because estimates from pilot studies alone tend to be underpowered due to the variability in estimated standard errors,^{19,20} we will combine our results (including the ICC) with clinically meaningful effect and results of previous adequately powered interventions to calculate sample size requirements for our large cluster RCT. Data from the recruited pediatric practices show that 5-7 very poorly controlled asthmatics are seen per month.

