Statistical Analysis: To assess feasibility outcomes in Aim 1, we will estimate parameters relevant for planning a larger study, including standard deviations of outcomes and ICC. We will also conduct preliminary analyses of the impact of Asthma Link™ on asthma outcomes. We will compare participants in the two arms (Asthma Link™ and comparison group), using methods such as parametric or nonparametric t-test or Poisson regression, depending on the observed outcome distribution. Some outcomes may have a Poisson distribution, such as hospital admissions, while spirometry values may be continuous. Intent-to-treat and completer analyses will be performed. The data collected in this proposal will provide estimates of trial retention, ICC, standard deviation, and effect size. We will use these and data published in the literature to estimate sample size for a larger trial. The secondary outcomes analyses of asthma health outcomes will be exploratory by necessity given the pilot nature of this study.

INVESTIGATOR STUDY PLAN

Data will be collected at baseline (study entry), and at 3-, 6-, and 12-month follow-up in the privacy of the parent/child's home as the parent/child survey will be sent through email, in the pediatric practice staff's office or home (for pediatric provider and asthma champion surveys which will be sent through email), in the school nurse office or home (for school nurse surveys which will be sent through email). Assessments will be pre-tested to ensure the time burden does not exceed 30 minutes. The parent/student survey and assessment tools for this study will be adapted from [name] prior adolescent smoking cessation trials and our pre/post study^{14,18}. Data confidentiality will be emphasized on the surveys and verbally by Research Coordinator, and by the use of a unique study identification number.

Data Management: The surveys will be conducted either over the phone or by using the REDCap™ system, a nationally used secure, web-based database application (<http://project-redcap.org>) that provides: 1) an intuitive interface, 2) audit trails for tracking data manipulation and export, 3) procedures for importing data from external sources, 4) easy development of web survey tools and 5) automated export procedures to various statistical packages.

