25. LOCAL NUMBER OF SUBJECTS

200 parents and children in grades 1-12 (aged 6-17 years) (i.e. 100 parent-child dyads total) with asthma will be recruited from the practices (25 parent-child dyads/practice) to achieve a retention of N=144 parents and children (i.e. 72 parent-child dyads) at the end of the study (from the 4 practices) at 12 month follow-up.

If two siblings are eligible for Asthma Link and this study, both children may participate in Asthma Link clinical program but only one child per family may be allowed to participate in the research study. We will grant the parent/guardian permission to choose which child they would like to participate in the research arm of the study.

Up to 16 Pediatric providers participating in Asthma Link™ will be recruited from the participating practices to participate in this study.

Up to 50 School nurses participating in Asthma Link™ will be recruited from the schools that the children participating in the study attend to participate in this study.

Up to 4 Asthma Champions participating in Asthma Link™ will be recruited from the participating practices to participate in this study.

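### The intent-to-treat and completer sets are undefined and no missing-data method is named, so for ACT, symptom days and FEV1 at 12 months the two analyses may nearly coincide

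*Combined protocol and SAP*

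**What the plan says.** Section 13 (Statistical Analysis) says the arms will be compared "using methods such as parametric or nonparametric t-test or Poisson regression, depending on the observed outcome distribution", and then that "Intent-to-treat and completer analyses will be performed". It does not define either set. It mentions no imputation, repeated-measures model, follow-up-time offset or sensitivity analysis for missing values. It calls the health-outcome analyses exploratory.

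The same section sets the schedule: "Data will be collected at baseline (study entry), and at 3-, 6-, and 12-month follow-up". No single time point is named for the health-outcome comparison.

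On losses, section 13 (Sample size calculation) says: "In order to obtain a sample size of 72 parent-child dyads to complete the research, we will potentially enroll up to 100 parent-child dyads". Section 25 repeats this as 100 dyads recruited "to achieve a retention of N=144 parents and children (i.e. 72 parent-child dyads) at the end of the study", at 12 months. Section 13 also gives planning figures for retention: "For a conservatively low retention rate of 80%, lower than the 97% observed in" a previous study. Section 11 reads differently: "Recruitment will be performed from each practice site until the target n=72 parent-child dyads (18 per site) are recruited", which leaves no allowance for loss.

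Section 11 shows where each outcome comes from. ACT and symptom days come from parent surveys. FEV1 comes from portable spirometry at school. Emergency visits, admissions and steroid courses are also read from the medical record, and refills from the pharmacy. Absences come from the school nurse as well as the parent (sections 10 and 11).

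**The concern.** Naming two analyses suggests that comparing them will show whether dropout has affected the result. That works only if the intent-to-treat analysis uses information from children whom the completer analysis leaves out. A t-test or rank test at 12 months cannot do so: a child with good 3- and 6-month values but no 12-month value drops out of both. The open wording of the method list does not exclude a better method, but none of the methods named uses the follow-up visits together.

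If the two results agree because they rest on the same children, the agreement says nothing about bias. Section 13 also intends to carry standard deviations and effect sizes forward, alongside published data, to plan the larger trial. Estimates for the survey and spirometry outcomes would then describe mainly the children who stayed.

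**Working it through.** **1. The planned allowance.** Inputs: 100 dyads enrolled and 72 retained (sections 13 and 25).
- Loss = 1 − 72/100 = 28%. The same follows from 144/200 people and, per practice, from 18/25.
- Enrolment needed = 72/(1 − loss). At 28% this gives 72/0.72 = 100, the stated figure. The check is circular, because 28% is itself derived from 100 and 72.
- At the plan's 80% retention: 72/0.80 = 90. At 97%: 72/0.97 = 74.2, so 75. Neither gives 100.

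So 28% is a ceiling, and the plan's own retention figures imply 20% or 3%.

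**2. Who is in a 12-month two-sample test.** At the ceiling, 36 of 50 children per arm have a value. Ignoring clustering, the standard error of a mean difference is √(2/50) = 0.200 SD with everyone and √(2/36) = 0.236 SD with those retained, a ratio of 1.18.

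**3. Simple bias formula.** If only one arm's lost children differ from its retained children, bias = fraction missing × gap between retained and lost. The gap is an assumption; the documents give none.

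| Fraction missing | Gap 0.25 SD | Gap 0.5 SD |
|---|---|---|
| 0.28 | 0.07 | 0.14 |
| 0.20 | 0.05 | 0.10 |
| 0.03 | 0.008 | 0.015 |

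**4. Simulation.** 4,000 trials per setting, 50 children per arm, no true effect, three equally correlated visits (correlation 0.5 to 0.7), no clustering. Where dropout is outcome-related, children worse at 6 months are more likely to leave (log-odds 0.5 to 1.0 per SD). All of these are assumptions.

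| Dropout pattern | Bias of 12-month two-sample comparison (SD) |
|---|---|
| Same mechanism, 28% in each arm | about 0.001 |
| Outcome-related in one arm only, 3% in each arm | 0.01 to 0.02 |
| Same mechanism, 20% against 36% | 0.04 to 0.09 |
| Outcome-related in one arm only, 20% in each arm | 0.05 to 0.12 |
| Outcome-related in one arm only, 20% against 36% | 0.09 to 0.22 |

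In the last pattern, a likelihood analysis using the 3- and 6-month values has bias below 0.01 SD and a spread of 0.22 to 0.23 SD, against 0.23 to 0.24 SD for the two-sample comparison. The small bias follows from the set-up, since dropout was made to depend on a 6-month value that the analysis uses. When dropout in that arm depends on the unseen 12-month value instead, the likelihood analysis is itself biased by 0.12 to 0.14 SD in the two extreme settings (correlation 0.5 with log-odds 0.5, and 0.7 with 1.0).

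**The case against.** The strongest reply is that the plan leaves the method unspecified and does not commit to the wrong one. The list is open and includes Poisson regression. Completer is undefined: if it means completing the programme, intent-to-treat by randomised practice differs from it even with no missing data. At 3 and 6 months, children lost later still contribute. All of this stands, and it is why the two analyses may coincide and need not.

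Outcome sources narrow the point further. A reader might infer that every intent-to-treat result would be a second completer result. Section 11 does not support that: emergency visits, admissions, steroid courses and refills can be obtained for families who stop answering surveys, unless they withdraw permission. Absences also have a nurse report. FEV1 is measured at school, so an unanswered survey does not by itself lose it.

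A reader might also infer that unequal, outcome-related dropout is likely because only one arm has a daily nurse visit. Section 11 does time spirometry to that visit, which leaves open how comparison children are reached. But surveys go out by email or telephone and the gift cards (section 24) are the same for all dyads. No passage says that dropout will differ by arm or that sicker children will leave.

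Finally, the analyses are secondary and exploratory, retention is itself a primary outcome with reasons for dropout recorded, and section 13 does not rely on pilot effect sizes alone. This limits the consequence but does not supply the missing definitions.

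**Conclusion.** The point holds in a limited form. The two analysis sets are undefined and no missing-data method is named. For ACT and symptom days, and for FEV1 when a child is not tested, a 12-month two-sample comparison would use nearly the same children under either label. Twelve months is taken here because it is the last survey and the time of the retention target; the plan does not single it out.

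Up to 28% may be missing under the enrolment allowance, and 20% or 3% under the plan's retention figures. The 28% should not be read as an expected loss. Bias runs from about 0 to about 0.2 SD depending on assumed dropout. The upper end needs heavy loss, a 16-point imbalance (36% − 20%) and outcome-related dropout in one arm only, and even then it is about one standard error. It should not be quoted as the likely bias. This is a modest improvement to an exploratory analysis, and it does not threaten the feasibility aims.

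**What to change.** In section 13:
- Define intent-to-treat as all enrolled children analysed by the arm to which their practice was randomised, and say whether completer refers to the programme or to follow-up.
- For ACT, symptom days and FEV1, use a repeated-measures linear mixed model over 3, 6 and 12 months with arm-by-visit effects, baseline as covariate and a term for practice. Practices are nested within arm, so this should be a random effect, with a note that four practices limit inference.
- Report by arm how many children have no follow-up value, since they add nothing to this model.
- Keep the completer analysis as a labelled sensitivity analysis.
- Reconcile the section 11 target of 72 recruited with the 100 enrolled in sections 13 and 25, so that the planned loss is clear.

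The cost is a few lines of text and a little more analysis work; no extra visits, data or participants are needed. The model relies on data being missing at random given baseline and earlier visits. It does not remove bias if dropout depends on unobserved 12-month values.

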14. PROVISIONS TO MONITOR THE DATA TO ENSURE THE SAFETY OF SUBJECTS*

Potential Risks and Adequacy of Protection Against Risks. The interventions (both Asthma Link™ and Enhanced Usual Care) in this proposal are state-of-the-art, developed by a Pediatric Pulmonologist and represent good standards of care as recommended by the National Asthma Education and Prevention Program and the American Academy of Pediatrics and the American Academy of Asthma, Allergy, and Immunology. Asthma Link™ practices are evidenced-based and have not shown any adverse events in multiple prior studies.^{13,14} The potential risks of the evaluative research component of this project are minimal. Some participants may have concerns about the confidentiality of their surveys and study records. The Research Coordinator and Primary Investigator will emphasize the confidentiality of all data collected and reassure and address any participant with concerns. Participant confidentiality will be maintained through a number of strategies. Each participant will be assigned a unique study identification (ID) number. Any link between the unique study ID and participant identifiers such as demographics, asthma health data, and questionnaire data will only be accessible to the Primary Investigator and Research Coordinator responsible for data collection and will be maintained in a secure, encrypted, password-protected, HIPAA compliant research drive. Other UMMS personnel will not be privy to identifying information about the individual participants and the link between study ID and identifiers will otherwise be destroyed. Given the minimal risk nature of this study, a data monitoring committee would not be necessary.

All data stored within computer files will be password protected behind a firewall to ensure that access is available only to those directly involved in the study analysis. Only data that has been stripped of all personal identifying information is made available to the data management (e.g. RedCap) systems;

At study completion, the link between the identifying information and their data will be destroyed, as will be contact information.

Finally, all study staff will complete the CITI Course in the Protection of Human Research

INVESTIGATOR STUDY PLAN

Subjects and Good Clinical Practices online training in research ethics to ensure that all staff are compliant with confidentiality training.

Monitoring Adverse Events.

The principal investigator and research coordinator will be responsible for monitoring adverse events during the study, with [name] assuming this responsibility if these individuals are unavailable. The role of the responsible person is 1) to identify the concern through assessing for health changes at each survey; 2) develop an appropriate response that involves consultation whenever possible to alleviate or minimize any adverse event (AE); and 3) to ensure that the adverse event is reported in a timely manner to the responsible authority. We will collect adverse events that are volunteered spontaneously during interactions with participants. Participants will be monitored for occurrence of events defined as any undesirable experience or unanticipated benefit. Events may occur during recruitment, intervention deployment, and follow-up assessments. Based upon previous research in school-supervised asthma therapy, we anticipate that adverse events or experiences will be rare. The Principal Investigator will assess whether an undesirable experience or unanticipated problem occurred (adverse event) and will record details of all adverse events on an adverse event case report form.

Although our study poses minimal risk to subjects and no adverse events are expected due to the nature of the study, we will follow the adverse event procedure of the University of Massachusetts Medical School. The current policy for reporting unanticipated problems and adverse events for the protection of human subjects in research at the University of Massachusetts Medical School is as follows:

“All adverse events involving risk to subjects or others that are serious and unanticipated and related to the study procedures must be reported, using the applicable Prompt Reporting Form, within 48 hours of the investigator becoming aware of the event.

All unanticipated problems which are unexpected and suggest that the research places subjects or others at a greater risk of harm and are related to the research must be reported, using the applicable Prompt Reporting Form, within 48 hours of the investigator becoming aware of the event.

In certain situations, this requirement for prompt reporting may necessitate the submission of a report before all information has been collected. In these situations, a preliminary report may be submitted with a follow-up report submitted at a later date when more information is available.

Events/problems which are not serious, are anticipated and not related to the study procedures must be reported in summary format at the time of continuing review.”

Adverse events that do not meet the requirements of prompt reporting will be provided at the time continuing review is submitted. The continuing review form in the UMMS eIRB will request this information.

We do not anticipate that any serious adverse events (death, life threatening illness, new serious or permanent disability) will occur. However, should such an event occur, the Principal Investigator will report the event within 24 hours of initial receipt of information to the University of Massachusetts IRB and NHLBI program officer. Other serious and unexpected AEs related to the study will be reported to the Program Officer within 5 days. Unanticipated

INVESTIGATOR STUDY PLAN

problems (that are not serious AEs) will be reported to the UMass IRB and the NHLBI Program Officer within 14 days of becoming aware of the problem. Any reports sent to the funding agency about the event will be included in the report to the IRB.

The adverse event case report form will include a description of all undesirable experiences, required interventions, and an assessment of the subject after the event if possible. An estimate of the extent of injury, and prevention strategies will be reported. The Principal Investigator will classify the relationship of the study protocol to the event as follows:

- Not related: The event is clearly related to factors such as the participant's clinical state, not with the study protocol.
- Remote: The event was most likely related to factors such as the participant's clinical state, not with the study protocol.
- Possible: The event follows a reasonable temporal sequence associated with participating in the study and/or is consistent with events related to receiving the intervention but is possibly related to factors such as the subject's clinical state.
- Probable: The event follows a reasonable temporal sequence associated with participating in the study and/or is consistent with receiving the intervention and cannot be reasonably explained by factors such as the subject's clinical state. The severity of an adverse event in both groups is defined as a qualitative assessment of the degree or intensity of an adverse event as determined by the principal investigator as follows:
- Mild: No impact (in anyway) on the participant.
- Moderate: Impacts on the participant but is not life-threatening or incapacitating.
- Severe: Fatal, life threatening, permanently disabling; severely incapacitating; requires immediate medical evaluation.

All adverse events will simultaneously be reported to institutional officials. The report will summarize the facts of the case, including the date and a description of the participant; whether the event is related to the study's protocols; the steps that have been taken to address the issue; whether the event provides emerging knowledge about the risks of the study that should be conveyed to respondents; and whether the consent form should be revised.

Anticipated Adverse Events.

Given that this is a minimal risk study, a data monitoring committee and/or a data safety monitoring board is not required for this study. An adverse events log is inappropriate for this type of study. Alternatively, the PI will periodically examine the data and should any research-related unexpected events arise, the PI will evaluate the event per the procedure listed above and will adhere to the institution's prompt reporting requirements. We do not anticipate any adverse events from this study as the primary procedures involve minimal risk surveys, checklists and routine clinical spirometry.

In this research, the risks that result from study participation are considered minimal as the research is primarily evaluative with the use of surveys and performance of spirometry. The major risks are:

- Risk of loss of confidentiality: The protections against confidentiality loss have been described. The PI is principally responsible for ensuring that there is no loss of confidentiality during the course of the study. Any loss that occurs despite these protections will be evaluated on an individual basis.

INVESTIGATOR STUDY PLAN

- Risk of Spirometry: Spirometry is a routine, non-invasive clinical test that is commonly performed in children with asthma. This test has been used both clinically and in research without any adverse events.^{23,24} There are no risks associated with spirometry except for the potential for a slight dizzy feeling and/or temporary cough. These symptoms are not always present and are temporary. In order to minimize risks, the participant will be in a seated position with adult supervision and a trained technician will perform spirometry, with physician available by phone for concerns or questions. We will follow institutional policies for prevention of Covid transmission, which includes the technician wearing a surgical mask with eye protection and using a new disposable mouthpiece for each participant. For this study the test is performed without the intent of yielding direct health benefit.
- Risk of discomfort while answering questions: Some subjects may feel uncomfortable answering certain survey questions (e.g., questions about family income) however subjects will be notified that they are welcome to skip questions or withdraw from the study at any time without penalty.

Given that this is a minimal risk study, the only foreseeable risks to the subjects include the possible loss of confidentiality. To address this, all participants will be given information on ways to contact [name] and the University of Massachusetts Medical School IRB

Data and Safety Monitoring Board (DSMB)

Given that this is a minimal risk study (wherein participants agree to enroll in the study after they become part of the Asthma Link program if they are in the Asthma Link practices or after they fit study inclusion criteria if in the Enhanced Usual Care practices), participants will primarily be evaluated through surveys, interviews, and spirometry, and therefore a data monitoring committee and/or a data safety monitoring board is not appropriate for this study. Alternatively, the PI will periodically examine the data and should any research-related unexpected events arise, the PI will evaluate the event per the procedure listed above and will adhere to the institution's prompt reporting requirements. We do not anticipate any adverse events from this study as the primary procedures involve minimal risk surveys, checklists and routine clinical spirometry.

This research is not designed to discover incidental findings and therefore we do not plan to follow up on incidental findings

